### 3.2.2 Follow-up Period

After titration, all participants will receive Dose Level 3 of study drugs at the target dosages (sacubitril/valsartan 200 mg BID or enalapril 10 mg BID) if they tolerate them. Dose Level 3 should be maintained until the end of the study.

Participants who no longer tolerate the target dosages at any time during the course of the Follow-up Period may be down-titrated to the nearest lower dosage at the Investigator's discretion.

Before considering down-titrating the dosage of study drug to the nearest lower dose level, the Investigator should consider reducing non-disease-modifying medications (e.g., calcium channel blockers, diuretics, nitrates, and  $\alpha$ -blockers) to rectify the situation. Every attempt should be made to re-challenge the participants so that they are kept on the maximal tolerated dose of study drug for as long as possible throughout the Follow-up Period.

If study drug is temporarily discontinued, it should be reintroduced as soon as it is medically justified. Study drug discontinuation for any reason after Randomization, will not constitute withdrawal from the study. Participants are expected to attend all the protocol-specified study visits to perform all assessments as stipulated in the visit schedule, unless they do not want to continue in the study or withdraw consent. For participants who do not wish to continue with the protocol specified assessments, before withdrawn completely from the study, should be offered some modified follow-up, e.g., by less frequent visits, a final in-person visit with telephone follow-up for other planned visits, telephone follow-up alone, follow-up through contact with the primary care physician or through medical records etc.

The study will end when at least 302 events have occurred (CV death or first HF hospitalization) and when all participants have a minimum follow up of 3 months. However, based on the planning assumptions (see [Section 12.8](#)) the overall study duration estimated to achieve the 302 events will be approximately 36 months, with a projected recruitment period of approximately 18 months and a follow-up period of 18 months after the enrollment of the last participant.

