## 9 Study discontinuation and completion

### 9.1 Discontinuation

#### 9.1.1 Discontinuation of study treatment

Discontinuation of study treatment for a participant occurs when study treatment is permanently stopped for any reason (prior to planned duration), and can be initiated by either the participant or the Investigator.

The Investigator must discontinue study treatment for a given participant if, he/she believes that continuation would negatively impact the participant's well-being.

Study treatment must be discontinued under the following circumstances:

- participant decision
- pregnancy
- use of prohibited treatment as per recommendations in the prohibited treatment section
- any situation in which study participation might result in a safety risk to the participant
- any laboratory abnormalities that in the judgment of the Investigator, taking into consideration the participant's overall status, prevents the participant from continuing participation in the study

If discontinuation of study treatment occurs, the Investigator should make a reasonable effort to understand the primary reason for the participant's premature discontinuation of study treatment and record this information.

Participants who discontinue study treatment or who decide they do not wish to participate in the study further should NOT be considered withdrawn from the study UNLESS they withdraw their consent (see withdraw of informed consent section.). **Where possible, they should return for the assessments indicated** in the assessment schedule. If they fail to return for these assessments for unknown reasons, every effort (e.g., telephone, e-mail, or letter) should be made to contact the participant/pre-designated contact as specified in the lost to follow-up section. This contact should preferably be done according to the study visit schedule.

If the participant cannot or is unwilling to attend any visit(s), the study site staff should maintain regular telephone contact with the participant, or with a person pre-designated by the participant. This telephone contact should preferably be done according to the study visit schedule.

After study treatment discontinuation, at a minimum, in abbreviated visits, the following data should be collected at clinic visits or via telephone/email contact:

- new/concomitant treatments
- adverse events/SAEs

The Investigator must also contact the IWRS to register the participant's discontinuation from **study treatment**.

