After 3 weeks, at Visit 102, initial dosages will be up-titrated for an additional 3 weeks to Dose Level 2 or to the target Dose Level 3 (enalapril 10 mg BID or sacubitril/valsartan 200 mg BID) if they tolerate it.

Visit 103

Patients receiving Dose Level 2 will receive Dose Level 3 for 3 weeks at Visit 103 if they tolerate it.

End of Study (EOS) (Visit 199)

The study will be completed when reaching 302 patients with CV events or if a recommendation is made by the DMC to prematurely stop the study. At the end of the study, all participants will return for the final end of study (EOS) visit (Visit 199)

Study completion

Study completion is defined as when the last subject finishes their End-of-study Visit, and any repeat assessments associated with this visit have been documented and followed up appropriately by the Investigator, or in the event of an early study termination decision, the date of that decision (e.g., each subject will be required to complete the study in its entirety and thereafter no further study treatment will be made available to them).

Baseline

Baseline value is the last non-missing assessment before the first administration of study drug, unless specified otherwise.

Last Contact

Last contact is set as the data of the latest performed visit, in several cases the End-of-study Visit. The last contact date will be used for censoring patients in the analysis of time to events endpoints.

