2.4 Treatments

2.4.1 Study treatment

The overall duration of exposure will be summarized by the treatment arm. The number of patients who do not tolerate the target dosage and will be titrated down to the lower dose level will be summarized and listed by the treatment arm. The FAS and SAF will be used for this analysis.

The overall duration of exposure to study treatment (sacubitril/valsartan or the active control enalapril) will be calculated in days as: (Date of last administration of study treatment) – (Date of first administration of study treatment) + 1 in each visit interval, and then summed within each level of study medication. The calculation logic shall be as follows for each entry (rows) of intervals within visits:

- For the rows, if the Enalapril_ongoing/Sacubitril_ongoing is 1 (Ongoing) and the next visit Start date is available then we impute End date with available Next visit Enalapril/Sacubitril startDate.
- For rows where end date is missing and the next visit is missed and if its ongoing dose we impute with Start date of same record.
- For the row in the Dosage administration data if the end date is missing and if the dose is not ongoing, we will impute it with corresponding Sacubitril/Enalapril Start date.
- For the last row in the Dosage administration data, if the end date is missing and dose is Ongoing then to impute below date only if its after the dosing Start date :
 - Death date (if available),
 - Last known Patient Alive date
 - Max Visit date Information available
 - if any of the above date is not available then to impute the end date with start date of same record.

- If after all these steps, same inconsistency still generates negative dates (end dates before start dates), then this interval should be considered as zero days.

As the follow up time may vary between participants, the treatment adherence will be presented as percentage from total follow up time as well.

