2.5.2.1 Time to CV death

The time from randomization to CV death will be considered as censored at the final analysis for participants who have not experienced a CV death. The censoring date for those participants without CV death prior to the analysis time point will be the following:

- date of death from non-CV causes, if the patient died.
- date of withdrawal of informed consent, if the patient withdrew the consent;
- date of last visit otherwise;

It will be considered as CV death for all the cases classified by the CEC as:

- Fatal Myocardial Infarction (MI);
- Heart Failure;
- Sudden Death;
- Fatal Stroke;
- Fatal Pulmonary Embolism;
- Cardiovascular Procedure-Related Death;
- Resuscitated Sudden Cardiac Arrest;
- All Undetermined causes of death (Presumed Cardiovascular Death, Presumed Sudden Death, Unknown death)

The definitions used to classify these events are described in detail in the CEC Charter, Version 1.0 – November 3rd, 2020. The classification frequencies for each cause will be presented descriptively.

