2.5.2.2 Time to first HF hospitalization

The time from randomization to first HF hospitalization will be considered as censored at the final analysis for participants who have not experienced a HF hospitalization. The censoring date for those participants without a HF hospitalization prior to the analysis time point will be the following:

- date of death, if the patient died.
- date of withdrawal of informed consent, if the patient withdrew the consent;
- date of last visit otherwise

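### Event-free participants are censored at the last performed visit, but no matching cut-off is set for events found later by off-site follow-up

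*SAP*

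**What the plan says.** **Censoring date.** SAP 2.1.1 defines last contact: "Last contact is set as the data of the latest performed visit, in several cases the End-of-study Visit". It continues: "The last contact date will be used for censoring patients in the analysis of time to events endpoints". SAP 2.5.2.1 (CV death) puts death from a non-CV cause and consent withdrawal first, and for everyone else gives "date of last visit otherwise". SAP 2.5.2.2 (first HF hospitalization) ends the same way. SAP 2.6.2.5 carries the method over to the secondary endpoints. Protocol 12.4.3.1 and 12.4.3.2 also censor at the last visit, naming Visit 199.

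**Who is censored.** In SAP 2.5.2.1 the time is "considered as censored at the final analysis for participants who have not experienced a CV death"; in 2.5.2.2 it is "considered as censored at the final analysis for participants who have not experienced a HF hospitalization". Neither section, nor the pairwise algorithm in SAP 4.1, excludes an event dated after the last performed visit.

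**Follow-up without visits.** For participants who stop attending, protocol 3.2.2 offers telephone contact or "follow-up through contact with the primary care physician or through medical records". Protocol 9.1.1 adds that "the study site staff should maintain regular telephone contact with the participant". The remote-procedures text in protocol section 3 says that such contact should confirm whether endpoints have occurred.

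**A second date exists.** SAP 2.4.1 lists "Last known Patient Alive date" separately from the latest visit date, but uses it only to fill in missing dose end dates.

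**The concern.** Censoring should not depend on whether the participant later has the event. Suppose the last visit was at Month 8 and medical records show the participant alive and event-free at Month 30. The rule gives that participant 8 months of follow-up. Had the same records shown a CV death at Month 20, an event at Month 20 would be counted. One source of information is used when it brings an event and ignored when it does not.

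The rule reaches the first two tiers of the primary win ratio, the component Cox models, the composite of CV death or HF hospitalization, and all-cause mortality. At tier 1, the Month 8 participant cannot win against a comparator who dies at Month 24, although the records show survival beyond that date. The pair passes to the lower tiers, where it may still be decided. The primary estimand applies treatment policy to discontinuation (SAP 2.12.1), so follow-up after treatment stops is exactly what it relies on. Treatment is open-label, so the off-site share could differ by arm.

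**Working it through.** **Inputs from protocol 12.8.1.** Composite event rates of 0.20 (enalapril) and 0.16 (sacubitril/valsartan) per year; 66% of first events are HF hospitalizations; uniform accrual over 18 months and total duration 36 months, so follow-up is 1.5 to 3 years; 450 per arm; a 25% lower NT-proBNP ratio.

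**The plan's own event count.** With exponential times, expected events per arm = 450 × [1 − (e^(−1.5L) − e^(−3L)) / (1.5L)].
- L = 0.20: 450 × [1 − (0.7408 − 0.5488)/0.30] = 162.0
- L = 0.16: 450 × [1 − (0.7866 − 0.6188)/0.24] = 135.3
- Total 297.3, which is 1.6% below the stated 302. The inputs are close enough to use.

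**Simulation.** A share of each arm moves to off-site follow-up after a randomly chosen scheduled visit from Week 12 on and makes no further visit; events are still captured completely to study end. Three rules were applied to the same data:
- (a) censor at last ascertainment;
- (b) the rule as written: count all events, censor event-free time at the last visit;
- (c) cut both at the last visit.

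Assumed, because the documents give no figure: the off-site shares, off-site status independent of risk, and an SD of 0.8 for the log NT-proBNP ratio. There are no country strata. Win-ratio results rest on 150 simulated trials per scenario; rates and hazard ratios come from large samples.

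**Composite rate per 100 patient-years, (a) → (b)**

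| Off-site share | Enalapril | Sacubitril/valsartan |
|---|---|---|
| 5% | 19.94 → 20.40 (+2.3%) | 15.94 → 16.32 (+2.4%) |
| 10% | 20.01 → 20.93 (+4.6%) | 15.96 → 16.75 (+4.9%) |
| 15% | 20.00 → 21.46 (+7.3%) | 15.97 → 17.19 (+7.6%) |
| 20% | 20.03 → 22.00 (+9.8%) | 15.98 → 17.66 (+10.5%) |

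The mechanism shows in the enalapril arm at 10%. The 162.1 events are the same under both rules, but person-time falls from 162.1/0.2001 = 810 to 162.1/0.2093 = 774 years. Rule (c) restores the rate (19.98) but keeps only 153.4 events.

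**Effect measures with no true effect, (a) → (b)**

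| Off-site share, sacubitril/valsartan v enalapril | Composite HR | CV death HR | Win ratio |
|---|---|---|---|
| 10% v 10% | 1.002 → 1.001 | 1.005 → 1.004 | 0.998 → 0.999 |
| 10% v 5% | 0.998 → 1.022 | 0.999 → 1.027 | 1.003 → 0.989 (−1.4%) |
| 15% v 5% | 0.993 → 1.042 | 0.998 → 1.056 | 1.009 → 0.982 (−2.7%) |
| 5% v 15% | 0.995 → 0.949 | 0.991 → 0.936 | 1.004 → 1.032 (+2.8%) |
| 20% v 5% | 1.000 → 1.075 | 1.001 → 1.091 | 1.000 → 0.959 (−4.1%) |

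With a true composite hazard ratio of 0.80, the estimate moves from 0.797 to 0.839 at 15% v 5%, and from 0.794 to 0.757 at 5% v 15%.

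**Sensitivity to the timing of the last visit.** A separate simulation placed last visits uniformly over months 3 to 12. The enalapril rate at a 10% share then went from 0.200 to 0.212 per year (+6%). With no true effect and 5% v 15%, the win ratio went from 0.99 to 1.025.

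**The case against.** Several counter-arguments stand and limit the point.

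- **Telephone contacts may be visits.** Protocol 9.1.1 speaks of abbreviated visits whose data may come by telephone or e-mail, and protocol 3.2.2 of telephone follow-up in place of planned visits. If sites log these as performed visits, the telephone part largely disappears. Physician and records contact is nowhere called a visit, so that part remains.
- **Visit 199 repairs the loss.** Protocol 9.2 has all participants return for it. Anyone who does is censored there and loses no time.
- **That late events count is inferred.** It follows from censoring only those without the event and from the absence of a cut-off. No sentence says it outright.
- **The SAP did not create the rule.** The protocol also censors at the last visit.
- **A better date may not cure everything.** If deaths reach the site passively and survival is not actively checked, a last-known-alive date can still depend on outcome.

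A reader might infer that the treatment comparison is biased as it stands, or that a particular arm is penalised. The documents do not support that: they give no off-site share for either arm, and equal shares leave the hazard ratios and win ratio essentially unchanged. A reader might also infer that an affected participant can no longer win at all against someone who dies later. The hierarchy does not work that way, because an undecided tier-1 pair goes on to HF hospitalization and then NT-proBNP.

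**Conclusion.** The point holds in limited form. As written, the plan uses different cut-offs for events and event-free time among participants who never attend Visit 199 and whose off-site contacts are not logged as visits. In that group absolute event rates are inflated: about 2% to 10% overall if 5% to 20% of participants are affected. Bias in the treatment effect needs an imbalance between arms. A 10-point imbalance moves the win ratio by about 3% and the hazard ratios by 4% to 6%, either way. NT-proBNP dilutes the effect on the primary endpoint, so the Cox analyses are more exposed. All these sizes rest on assumed shares and complete off-site capture of events. This should be fixed before database lock, but nothing in the documents shows that it would change the trial's conclusion.

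**What to change.** In SAP 2.1.1, 2.5.2.1 and 2.5.2.2 (and so 2.6.2.5), apply one cut-off to events and event-free time:

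- **Death endpoints:** censor at the last-known-alive date from any permitted route, a date SAP 2.4.1 already names.
- **HF hospitalization:** censor at the last contact of any kind at which hospitalizations were ascertained, falling back to the last visit where no such date is recorded.
- Keep death and consent withdrawal as earlier stops, and state that telephone contacts count.
- List this in SAP section 3 as a change from protocol 12.4.3.
- **Sensitivity analysis:** cut both events and event-free time at the last performed visit.

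The cost is a little more programming and one more sensitivity run. The documents do not show that a date of last hospitalization ascertainment is recorded, which is why the fallback is needed. The outcome dependence that comes from passive reporting of deaths may not go away entirely.

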2.1.2 Randomization

Patients were randomized stratified by Country and according to ACEI/ARBs use (not treated, treated with low dosages, less than 50% of the target dosage, and at least 50% standard doses of ACEIs/ARBs).

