### **6.3.2 Treatment assignment, randomization**

At Visit 101, after confirming that the participant fulfills all the inclusion/exclusion criteria, the Investigator or his/her delegate will log in to IWRS a second time in order to randomize the participant to one of the treatment arms. The number that was assigned to the study site and participant will be used to link the participant to a treatment arm and will specify a unique medication number for the first package of study treatment to be dispensed to the participant.

The randomization numbers will be generated using the following procedure to ensure that treatment assignment is unbiased and concealed from participants and Investigator staff. A participant randomization list will be produced by the IWRS provider using a validated system that automates the random assignment of participant numbers to randomization numbers. These randomization numbers are linked to the different treatment arms, which in turn are linked to medication numbers. A separate medication list will be produced by or under the responsibility of the vendor ARO using a validated system that automates the random assignment of medication numbers to packs containing the study treatment.

The randomization scheme for participants will be reviewed and approved by a member of the Novartis Randomization Office.

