2.1 Data analysis general information

Statistical analyses will be performed by BCRI statistician using R software (version 4.4.1). The blinding of the randomized treatments will be maintained for the clinical trial team until the database has been locked and released for statistical analysis. An independent statistician will be performing the interim analysis of unblinded data for the DSMB meetings.

Summary statistics will be provided by treatment arm for the variables considered in the study. Continuous variables will be summarized using n, mean or median, minimum, maximum, standard deviation or interquartile range. Categorical variables will be summarized using absolute and relative frequency.

Analysis will be performed after data lock when at least 302 participants with events have occurred (CV death or first hospitalization for HF) and when all patients have a minimum follow up of 12 weeks or if a recommendation is made by the Data Monitoring Committee (DMC) to prematurely stop the study.

Data from all sites will be analyzed together with treatment as fixed-effect factor and stratified by country.

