2.2 Analysis sets

Randomized Analysis Set (RAN)

RAN consists of all randomized participants.

Full Analysis Set (FAS)

FAS comprises all participants to whom study treatment has been assigned at randomization. According to the intent to treat principle, participants will be analyzed according to the treatment they have been assigned to during the randomization procedure. Randomization was stratified by country.

However, patients who did not qualify for randomization but were inadvertently randomized into the study and did not receive study medication will be excluded from FAS. Further exclusions from the FAS may only be justified in exceptional circumstances (e.g., serious GCP violations). These potential incidences imply the possibility that the FAS may be smaller than the RAN.

Safety Set (SAF)

SAF includes all participants who received at least one dose of study treatment. Participants will be analyzed according to the study treatment they actually received, where treatment received is defined as the randomized/assigned treatment if the subject took at least one dose of that treatment or the first treatment received if the randomized/assigned treatment was never received.

Per-Protocol Set (PPS)

PPS is a subset of participants of the FAS and will include participants with no major protocol violations and who took at least one dose of the study treatment. Patients with any of the following protocol violations will be excluded from the PPS, but not limited:

- Not fulfilling all the inclusion criteria as described on CLCZ696B3302 Protocol last version;
- Fulfilling any of the exclusion criteria as described on CLCZ696B3302 Protocol last version;

PD definition will be done according to BCRI Work Instruction IT RE 012.

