2.5.2 Statistical hypothesis, model, and method of analysis

The following primary analysis will be tested as (Wang and Pocock, 2016):
H0: $\Psi \leq 1$ (win ratio ≤ 1) - The true number of 'winners' for sacubitril/valsartan is less than or equal to the true number of winners for enalapril.

H1: $\Psi > 1$ (win ratio > 1) - The true number of 'winners' for sacubitril/valsartan is larger than the true number of winners for enalapril.

The primary efficacy endpoint will be analyzed using the win ratio approach (Pocock et al 2012), with treatment as fixed-effect factor and stratified by country (Dong et al. 2017). Every patient in the sacubitril/valsartan arm will be compared to every patient in the enalapril arm within each stratum (country). All pairs will be compared first by time to CV death; if there is no winner, they will be compared for time to first HF hospitalization; if again there is no winner, they will be compared according to reduction in NT-proBNP levels between randomization and Week 12. If the comparison between changes in NT-proBNP levels does not result in a winner, the respective pairwise comparison is tied. When comparing the time to an event between two participants and at least one of the times is censored, the comparison is only performed up to the censoring time. The comparison of NT-proBNP is performed based on the relative change between randomization and Week 12 and takes into account that relative changes within $\pm 25\%$ are considered medically irrelevant; in detail, let x_{LCZ696} and x_{Enal} be the relative changes of participants in the sacubitril/valsartan and the enalapril arm, respectively. Then, a comparison of NT-proBNP is in favor of the subject in the sacubitril/valsartan arm if $x_{LCZ696} < 0.75 x_{Enal}$. On the other hand, the comparison is in favor of the subject in the enalapril arm if $x_{Enal} < 0.75 x_{LCZ696}$.

The win ratio is estimated by the ratio of the number of winners in the sacubitril/valsartan group and the number of winners in the enalapril group with weights defined as the reciprocal of the stratum (country) sample size.

$$\Psi = \frac{\sum_m^M w^{(m)} n_{LCZ696}^{(m)}}{\sum_m^M w^{(m)} n_{Enal}^{(m)}}$$

Where $n_{LCZ696}^{(m)}$ and $n_{Enal}^{(m)}$ are the total number of wins in the m^{th} stratum for the sacubitril/valsartan and Enalapril groups, respectively; $w^{(m)} = 1/N^{(m)}$ and $N^{(m)}$ is the total sample size in the m^{th} stratum.

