2.6.2 Statistical hypothesis, model, and method of analysis

2.6.2.1 Analysis of time to events endpoints

The time from randomization to

- the first composite event of CV death or HF hospitalization,
- all-cause mortality, and
- to sudden death or resuscitated sudden cardiac arrest

will be analyzed using Cox's proportional hazards model with treatment as fixed-effect factor and stratified by country. The estimated hazards ratio and the corresponding 2-sided confidence interval will be provided for the FAS.

The Kaplan-Meier curves by treatment arm will be presented for the FAS. Additionally, the frequency and percentage of patients with a composite CV event will be provided by treatment arm.

Proportional hazard assumptions will be tested by weighted residuals diagnostics and by visual inspection. Alternative parametric survival models (Exponential, or Weibull, or Log-logistic, or log-normal survival models) will be used if

the risk proportional assumption did not meet. The model with the best likelihood function will be chosen in that case.

2.6.2.2 Analysis of number of visits to an ER due to HF that needs intravenous drugs

The rate of visits to an ER due to HF that needs intravenous drugs will be analyzed using a generalized linear model assuming a negative binomial distribution. The time at risk for a subject is the length of follow-up. The analysis model will include terms for treatment and country as fixed-effect factors and log (follow-up duration) as the offset. An estimate of the ratio of event rates between the treatment arms, together with the 95% confidence interval, will be presented for the FAS.

The number of visits to an ER due to HF that needs intravenous drugs during the treatment period will be summarized by treatment arms.

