2.6.2.3 Analysis of number of days alive out of the hospital

The duration in days of hospital-free survival within 1 year from randomization will be summarized by treatment group, and descriptive statistics (N, mean, standard deviation, median, and quartiles) will be provided. The mean difference between treatment groups will be compared using linear regression model with treatment as fixed factor adjusted for country. The estimated within treatment means, between-treatment difference and 95% confidence interval will be provided for FAS.

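### The SAP gives two accounts of the randomisation strata, and no efficacy model accounts for the prior ACEI/ARB stratum that one of them names

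*SAP*

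**What the plan says.** On the randomisation itself:

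- SAP 2.1.2: "Patients were randomized stratified by Country and according to ACEI/ARBs use". The levels follow in brackets: "not treated, treated with low dosages, less than 50% of the target dosage, and at least 50% standard doses of ACEIs/ARBs". The punctuation is loose; I read three levels (none, low dose, at least half of standard dose).
- SAP 2.2, under the Full Analysis Set: "Randomization was stratified by country". ACEI/ARB use is not mentioned.
- Protocol 6.3.2 describes the mechanics ("A participant randomization list will be produced by the IWRS provider using a validated system") but names no stratification factor.

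On the analysis:

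- SAP 2.1 sets the general rule: "Data from all sites will be analyzed together with treatment as fixed-effect factor and stratified by country".
- SAP 2.5.2 forms win-ratio pairs within country, as Protocol 12.4.2 does. SAP Appendix 4.1 lists four strata (Argentina, Brazil, Colombia, Mexico) and resamples within arm and stratum.
- The secondary Cox models in SAP 2.6.2.1 use a "proportional hazards model with treatment as fixed-effect factor and stratified by country". The component Cox models in 2.5.3 do the same.
- The NT-proBNP ANCOVA (2.5.3), the negative binomial models (2.6.2.2 and 2.8) and days alive out of hospital (2.6.2.3, "linear regression model with treatment as fixed factor adjusted for country") carry country.
- The LWYY and joint frailty models (2.6.2.4) name no stratum or covariate of their own.
- Prior ACE inhibitor or ARB use appears in SAP 2.9 as a subgroup variable, without the dose levels of 2.1.2.

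SAP section 3, which lists changes from the protocol, does not mention the strata.

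**The concern.** An analysis normally conditions on the factors that the randomisation balanced. If it leaves one out, the standard error still counts between-stratum variation that the design has removed. When the factor predicts outcome, the interval is then wider than it need be.

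Here the factor is close to the endpoint. Prior ACEI/ARB dosage decides the starting dose level (Protocol 3.2.1, SAP 2.1.1), so it shapes exposure in the weeks before the Week 12 NT-proBNP sample, the third tier of the primary endpoint. A link with NT-proBNP change is plausible, but the documents do not quantify it.

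The second issue is prespecification. The SAP is the only document supplied that states the strata, and its two statements differ. A reader cannot tell which scheme was run. An unexplained mismatch between design and primary analysis invites argument about the choice of strata once results are known, the more so in an open-label trial.

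**Working it through.** **1. Why the direction is conservative.** For a simple difference in means with 1:1 allocation balanced within strata, let s_w² be the within-stratum variance and s_b² the variance between stratum means.

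- Actual variance of the estimate: about 4·s_w²/N.
- Variance reported if the stratum is ignored: about 4·(s_w² + s_b²)/N.
- Ratio of reported to true SE: √(1 + s_b²/s_w²), which is at least 1.

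The Appendix 4.1 bootstrap behaves in the same way. It fixes arm sizes within country but lets the number of participants at each ACEI/ARB level vary between resamples, although under SAP 2.1.2 the design controlled that number.

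**2. Check on the plan's own figure.** The inputs from SAP 2.11 are 450 per arm, rates of 0.20 and 0.16 per year, uniform accrual over 1.5 years, 3 years in total and no loss to follow-up. With exponential times:

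p(λ) = 1 − [exp(−1.5λ) − exp(−3λ)]/(1.5λ)

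- p(0.20) = 1 − (0.7408 − 0.5488)/0.30 = 0.3600
- p(0.16) = 1 − (0.7866 − 0.6188)/0.24 = 0.3006
- Events = 450 × (0.3600 + 0.3006) ≈ 297.3

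The plan states 302, so this is 1.6% lower. The figure is reproduced, and it does not depend on how the analysis is stratified.

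**3. The relevant comparison: 4 country strata (planned) against 4 × 3 = 12 country by ACEI/ARB strata.** Trials of 900 were simulated with the SAP rates, a Week 12/baseline ratio 25% lower on sacubitril/valsartan, the 0.75 win threshold, 1/N weights, and permuted blocks of 4 within country by ACEI/ARB. Both analyses were run on the same simulated trials, with a U-statistic variance for the log win ratio.

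Assumed, because the documents give no values: country mix 60/20/15/5%, ACEI/ARB mix 15/35/50%, SD of the log NT-proBNP ratio 0.6 to 1.2, event hazard ratio 1.0 to 4.0 between the extreme ACEI/ARB levels, and death hazard multiplied by 1 or 2 after HF hospitalisation.

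Power (600 trials per setting):

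| Criterion | 4 strata | 12 strata | Largest gap |
|---|---|---|---|
| SAP 2.11 success rule (win ratio significant and both hazard ratios below 1) | 81.8–86.5% | 81.2–86.5% | 0.6 points |
| Win ratio test alone | 90.5–99.8% | 89.5–99.7% | 1.0 point |

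Both largest gaps favour country alone, and both arise at SD 1.2 with no prognostic effect of the stratum. The plan's 85% cannot be matched exactly because it gives no NT-proBNP SD, but it lies within the simulated range.

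No treatment effect (2000 trials per setting, SD 0.8; Monte Carlo error √(0.025 × 0.975/2000) ≈ 0.35 points):

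| Prognostic HR | Type I, 4 strata | Type I, 12 strata | Mean SE / empirical SD, 4 strata |
|---|---|---|---|
| 1.0 | 2.4% | 2.6% | 0.082/0.082 = 1.00 |
| 1.5 | 2.7% | 2.8% | 0.083/0.081 = 1.02 |
| 2.5 | 2.2% | 2.6% | 0.083/0.079 = 1.05 |
| 4.0 | 1.9% | 2.4% | 0.083/0.077 = 1.08 |

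**4. Change in the estimate.** With a treatment effect and SD 0.8, the mean win ratio was 1.406 against 1.409 (4 against 12 strata) at prognostic HR 1.5, and 1.399 against 1.411 at 2.5.

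**5. Sparse cells.** Under the assumed mix, untreated participants in the smallest country number 900 × 0.05 × 0.15 ≈ 7, about 3 per arm.

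**The case against.** The strongest reply is that the premise is unproven. SAP 2.2 does not say country only, so it may be a short statement rather than a contradiction. Equally, it may be the correct one, and then the planned analysis already matches the randomisation. This stands: the documents cannot settle it, so the IWRS specification must be checked before either section is edited.

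The reply continues that stratifying by country is the protocol's own primary analysis, that 12 strata show no power gain, and that some cells would be nearly empty. This also stands, and it is a fair reason for keeping country alone as primary. It does not excuse leaving that reason unstated.

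A reader might infer more than the documents support:

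- **Bias.** Pairing an untreated participant with a full-dose one looks like confounding. If ACEI/ARB use was a stratum, such pairs arise about equally in both directions, so they add noise, not bias. Tier 3 also uses each participant's own Week 12/baseline ratio.
- **Material loss of power, or an inflated type I error.** The tables show neither.
- **Every analysis uses country only.** This is not literally so. The recurrent-event models, the SGLT2-inhibitor Cox model, Fisher's exact test and the Holter comparison name no country term, and the MRI models use site and participant. The accurate statement is that no efficacy model includes the ACEI/ARB stratum.

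**Conclusion.** The point holds as a matter of consistency and prespecification. The SAP's two statements of the strata must be reconciled, and the omission of ACEI/ARB use from every efficacy model needs either correction or a reason.

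The numerical stakes are small. If ACEI/ARB use was a stratum and is prognostic, the country-only standard error is too large by about 2% at a hazard ratio of 1.5 between extreme levels and about 8% at 4.0. Power and type I error stay close to plan, and the sample size and event target do not move.

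These sizes rest on assumed country and ACEI/ARB mixes, an assumed NT-proBNP SD and an assumed prognostic strength expressed through event hazards. They use a U-statistic variance in place of the SAP's percentile bootstrap. That the strata were those of SAP 2.1.2 is itself an assumption until the IWRS confirms it.

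**What to change.** Before unblinding:

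1. Confirm from the IWRS specification which factors and levels were used, and make SAP 2.1.2 and 2.2 agree.
2. If ACEI/ARB use was a stratum, add it as a stratum in the Cox and LWYY models and as a factor in the NT-proBNP ANCOVA, the negative binomial models and the days-alive regression.
3. Run the win ratio and its bootstrap within country by ACEI/ARB strata, with a preset rule for collapsing sparse cells. Either make this primary with country-only as sensitivity, or keep the protocol's country-only primary, state why, and prespecify the finer version as a sensitivity analysis.
4. If ACEI/ARB use was not a stratum, correct SAP 2.1.2; the models then need no change on this account.

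The cost is SAP wording and, if the factor was a stratum, a variable that the IWRS should already hold. The drawbacks are some sparse cells in small countries and a small shift in the estimated win ratio. Making the finer stratification primary would also be a late change to the protocol's primary analysis and should be recorded in SAP section 3.
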